5.8.2. Clinical Laboratory Measurements

5.8.3. Analysis of Vital Signs and Safety Laboratory Measures

Summary of vital signs including systolic blood pressure, diastolic blood pressure, heart rate, oxygen saturation, Temperature, Respiratory rate will be provided. In addition, local laboratory results will be summarized by abnormality(low/high) and normality. Listings will be provided for all the local laboratory results.

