#### **11.4.5.2. Other Safety (Vital Signs and Laboratory Tests)**

##### **Definitions**

The following definitions will be applied to laboratory parameters and vital signs:

The potentially clinically significant value (PCSV) criteria are defined as abnormal values considered medically important by the Sponsor according to predefined criteria/thresholds based on literature review and defined by the Sponsor for clinical laboratory tests and vital signs. The PCSV criteria will be provided in the SAP.

PCSV criteria will determine which subjects had at least 1 PCSV during the respective TEAE periods, taking into account all evaluations performed during the respective TEAE periods, including unscheduled or repeated evaluations. The number of all such subjects will be the numerator for the PCSV percentage.

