##### **Analysis**

The incidence of PCSVs at any time during the TEAE period will be summarized regardless of the baseline level, and again in participants without PCSV in the corresponding category at baseline.

Summary tables, shift tables based on baseline normal/abnormal and other tabular and graphical methods may be used to present the results for laboratory tests of interest. Summary of vital signs will be provided.

Listings will be provided for subjects meeting PCSV criteria.

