4.6.3. Vital Signs and Laboratory Tests

Standard vital signs including body temperature, blood pressure, and heart rate, comprehensive vital sign assessment including additionally include SpO₂ and respiratory rate will be collected. Temperature and SpO₂ will be collected. Local safety laboratory tests collect absolute neutrophil count, platelet count, hemoglobin, ALT, AST, total bilirubin, and creatinine at baseline visit as well as study visits days 29,85 and 169.

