5.8. Analysis of Safety Data

Secondary safety endpoints are

1. Proportion of participants with grade ≥ 3 treatment-emergent adverse events (TEAEs), during the EAP and follow-up period
2. Proportion of participants with TEAEs leading to study drug discontinuation, during the EAP and follow-up period
3. Proportion of participants with treatment-emergent serious adverse events (SAEs) during the EAP and follow-up period
4. Proportion of participants with adverse events of special interest (AESIs) during the EAP

For safety variables, the following observation periods are defined:

- The pretreatment period is defined as the time from the signing of the ICF to before study drug administration.
- The EAP is defined as the day from first dose of study drug to day 169 ± 7 days
- The Follow-up period is defined as the end of the EAP to the end of the Follow-up Period (ie, the last study visit).

The safety analysis will be based on the reported AEs and other safety information (clinical laboratory evaluations, and vital signs). The summary of AE results will be presented for each treatment group for each of three TEAE periods: treatment-emergent EAP (TEEAP), treatment-emergent follow-up period (TEFUP), and overall study period (i.e., combined across the TEEAP and TEFUP). For laboratory and vital sign results they will be presented for each treatment group for each of three periods: EAP, follow-up, and overall study period.

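### The SAP's safety-lab tables do not separate pre-existing from new or worsened abnormalities, and the protocol's PCSV analysis is dropped without being declared

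*SAP*

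**What the plan says.** Protocol 11.4.5.2 covers laboratory tests and vital signs together. It says "The PCSV criteria will be provided in the SAP". It commits to summarising PCSV incidence in two ways: regardless of baseline level, and "again in participants without PCSV in the corresponding category at baseline". It also commits to a listing: "Listings will be provided for subjects meeting PCSV criteria". Shift tables are optional: "Summary tables, shift tables based on baseline normal/abnormal and other tabular and graphical methods may be used".

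SAP 4.6.3 has seven local tests (neutrophils, platelets, haemoglobin, ALT, AST, total bilirubin and creatinine), collected up to and including "creatinine at baseline visit as well as study visits days 29,85 and 169". SAP 5.8.3 then says that "local laboratory results will be summarized by abnormality(low/high) and normality", and in the next sentence "Listings will be provided for all the local laboratory results". SAP 5.8 presents lab and vital-sign results by treatment group "for each of three periods: EAP, follow-up, and overall study period". The pretreatment period is defined in that same section but is not among the three.

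SAP 1.2.4, which records departures from the protocol's statistical section, mentions only that some exploratory efficacy endpoints will not be reported.

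**The concern.** Eligible participants include transplant recipients on immunosuppression, people with active haematologic malignancy, and people receiving alkylating agents or antimetabolites (Protocol 7.2.1). In such a population it is plausible that counts, liver tests or creatinine are outside the local range before any study drug is given. A table of low, normal and high on study mixes those participants with the ones whose values changed after dosing.

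There is a second loss. Low and high carry no severity. A participant just below range at baseline who then falls a long way is low both times, and the table shows nothing.

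The labs were added by the site memorandum of 21 October 2021 as an additional safety measure. The SAP Overview says that the study's objectives could not be achieved after early termination, so descriptive safety is most of what the study can still report. With about 16 to 17 participants per arm, a chance difference between arms at baseline could look like a drug effect or hide one.

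**Working it through.** The plan states no figure on this point, so there is none to reproduce. The check is a comparison of text, followed by an illustration on assumed rates.

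**Text, item by item**

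- PCSV thresholds: the protocol places them in the SAP. The SAP has none; PCSV appears only in its abbreviation list.
- PCSV incidence regardless of baseline: a commitment in the protocol, absent from the SAP.
- PCSV incidence among those without it at baseline: a commitment in the protocol, absent from the SAP.
- PCSV listing: a commitment in the protocol. The SAP replaces it with a listing of all local lab results, which is broader but has no flag.
- Shift tables: optional in the protocol, absent from the SAP.
- Vital signs: within the protocol's PCSV analysis. SAP 5.8.3 plans only a summary.
- Declaration in SAP 1.2.4: none.

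Baseline labs are collected (SAP 4.6.3) and baseline is defined for safety variables (SAP 6.1), but SAP 5.8.3 does not use either.

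**Illustration (assumed rates; the documents give none)**

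Let p be the share abnormal on a test at baseline, all assumed to stay abnormal, and q the share of the rest who become abnormal. Then:

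- share abnormal on study = p + (1 − p)q
- pre-existing part of that share = p / [p + (1 − p)q]

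Example: p = 0.30 and q = 0.10 give 0.30 + 0.70 × 0.10 = 0.37, and 0.30 / 0.37 = 0.81.

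| p | q = 5% | q = 10% | q = 20% |
|---|---|---|---|
| 10% | 14.5% abnormal, 69% of them pre-existing | 19.0%, 53% | 28.0%, 36% |
| 30% | 33.5%, 90% | 37.0%, 81% | 44.0%, 68% |
| 60% | 62.0%, 97% | 64.0%, 94% | 68.0%, 88% |

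Chance imbalance: 66 / 4 = 16.5, which agrees with the 16 to 17 per group in SAP 2.1. With X and Y independent Binomial(16, p), the probability that |X − Y| ≥ 3 participants at baseline is 13% at p = 10%, 33% at p = 30%, and 37% at p = 40% or 60%.

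**Paired data**

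These sums treat every participant as having a baseline and a post-baseline value. The documents do not say how many do. The memorandum is dated 21 October 2021, enrolment closed on 16 December 2021 (SAP Overview), and the close-out schedule (Protocol Table 2) has no safety-lab row. The usable number per arm may be below 16.

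**The case against.** A reader might infer that pre-existing and treatment-emergent abnormalities cannot be told apart at all, or that the SAP ignores baseline throughout. The documents support neither.

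- **Listings.** Every local result is listed. With 66 participants and seven tests, a reader can trace each person. This stands, but a listing gives no count by arm, and the protocol's baseline-conditional incidence would have done so.
- **Baseline elsewhere in the SAP.** SAP 6.4 summarises by-visit data by scheduled visit. Its Table 2 has a Baseline row, and the text after it allows unscheduled safety-lab values to supply a time point, baseline included. A by-visit table with a baseline row would fit this text and would show imbalance between arms. SAP 5.8 names only three on-study periods, so the layout is unclear. Even with a baseline row, separate counts at each visit do not link a participant's own values.
- **Laboratory TEAEs.** The site memorandum and SAP 1.1 provide for them, and the TEAE definition refers to baseline. This is a real second route, but a partial one: it rests on investigator judgement and leaves out events attributed to the underlying disease or its treatment, where cytopenias may well be placed. SAP 4.6.1 still describes the narrower targeted list.
- **Early termination.** Protocol 11.6 allows reduced reporting, and the PCSV text was written for a planned 8,752 participants. Dropping the analysis may therefore be permitted. However, Amendment 2 keeps safety laboratory values among the data to be summarised, and permission to reduce does not remove the need to record the reduction.
- **Shift tables are optional.** This is correct. Their absence alone is not a departure from the protocol; the missing PCSV incidence is.

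**Conclusion.** The point holds for the planned summary tables. SAP 5.8.3 replaces the protocol's PCSV analysis, for labs and vital signs, with low/normal/high lab counts and a vital-sign summary. SAP 1.2.4 does not record this, and no baseline-referenced table takes its place. As written, the by-arm lab tables do not distinguish an abnormality present before dosing from one that is new or worse. The information is not lost: it remains in the listings and, in part, in the laboratory TEAEs.

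The size is unknown. Over assumed baseline rates of 10% to 60% and new-abnormality rates of 5% to 20%, between 36% and 97% of on-study abnormals would be pre-existing. That range assumes that baseline abnormalities persist and labs are fully paired. It shows that the tables could be dominated by baseline status, not that they will be. It would also go too far to say that the reduction breaches the protocol, because Protocol 11.6 may permit it.

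**What to change.** - For each of the seven tests, add one by-arm table of baseline category against worst post-baseline category, among participants with both values, with that denominator shown. Use PCSV bands or CTCAE v5.0 grades in preference to low/normal/high, so that worsening within an abnormal range is visible.
- Report the number with a new PCSV among those without that PCSV at baseline, as Protocol 11.4.5.2 provides, and state the thresholds in the SAP.
- Keep the full listings.
- If the PCSV analysis for labs or vital signs is dropped on purpose under Protocol 11.6, say so in SAP 1.2.4.

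The cost is one extra table from data already collected and a set of stated thresholds. Cells will be sparse at 16 to 17 per arm or fewer, so the table is descriptive only.

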5.8.4. Analysis Other Safety Variables

For subjects who become SARS-CoV-2 positive and require medically attended visits to the emergency department (ED), urgent care center (UCC), or hospitalization starting from the timepoint of SARS-CoV-2 RT-qPCR positive and through the end of the study, will have the following parameters or occurrences (worst or most abnormal finding) during the medically attended visit/stay collected (eCRF).

A COVID-19-related medically-attended visit (MAV) will be defined as follows: hospitalization, ER visit, urgent care visit, physician's office visit, or telemedicine visit, with one of the reasons for the visit being COVID-19.

Medically-attended visits related to COVID-19, as determined by the investigator, will be recorded in the eCRF. Details will include at minimum:

- Type of visit (hospitalization, ER, urgent care, physician's office visit, telemedicine)
- Date of visit
- If hospitalized due to COVID-19, length of visit
- Reason (list all COVID-19-related clinical manifestation[s] that prompted the medically-attended visit)
- If hospitalized due to COVID-19, whether ICU care was given
- If hospitalized due to COVID-19, whether mechanical ventilation was required
- Treatments given for COVID-19 (including, but not limited to, supplemental oxygen, corticosteroids, remdesivir, baricitinib, etc)

A listing of subjects who have abnormal findings with any SARS-CoV-2 infection-related medically-attended visit will be provided including the corresponding study period information.

5.9. Analysis of Pharmacokinetic Data

The concentrations of casirivimab and imdevimab in serum over time will be summarized descriptively for each of the treatment groups by age group (subjects ≥ 12 years of age to < 18 years of age, ≥ 40 kg; and subjects ≥ 18 years of age). Associations between covariates that may impact PK of casirivimab and imdevimab and concentrations of the antibodies in serum may be evaluated as appropriate. No formal statistical hypothesis testing will be performed.

5.10. Analysis of Immunogenicity Data

5.10.1. Analysis of ADA data:

The immunogenicity variables described in Section 4.8 will be summarized using descriptive statistics. Immunogenicity will be characterized per drug molecule by ADA status, ADA category and maximum titer observed in participants in the ADA analysis sets. For samples confirmed as drug specific ADA positive, but found negative at the lowest titer dilution, the lowest dilution in the titer assay is imputed.

The ADA status of each participants may be classified as one of the following:

Positive

Pre-existing - If the baseline sample is positive and all post baseline ADA titers are reported as less than 9-fold the baseline titer value

Negative - If all samples are found to be negative in the ADA assay.

The ADA category of each positive participants is classified as:

Treatment-boosted - A positive result at baseline in the ADA assay with at least one post baseline titer result \geq 9-fold the baseline titer value

Treatment-emergent - A negative result or missing result at baseline with at least one positive post baseline result in the ADA assay. Patients that are treatment-emergent will be further categorized as follows:

Treatment-emergent is further sub-categorized as:

Persistent - A positive result in the ADA assay detected in at least 2 consecutive post baseline samples separated by at least a 16-week post baseline period [based on nominal sampling time], with no ADA-negative results in-between, regardless of any missing samples

Transient - Not persistent or indeterminate, regardless of any missing samples

Indeterminate - A positive result in the ADA assay at the last collection time point only, regardless of any missing samples

The maximum titer category of each participants is classified as:

Low (titer $<1,000$)

Moderate ($1,000 \leq$ titer $\leq 10,000$)

High (titer $>10,000$)

The following will be summarized by treatment group and ADA titer level:

- Number (n) and percent (%) of ADA-negative participants
- Number (n) and percent (%) of pre-existing participants
- Number (n) and percent (%) of treatment-emergent ADA positive participants
 - Number (n) and percent (%) of persistent treatment-emergent ADA positive participants
 - Number (n) and percent (%) of indeterminate treatment-emergent ADA positive participants
 - Number (n) and percent (%) of transient treatment-emergent ADA positive participants
- Number (n) and percent (%) of treatment-boosted ADA positive participants

Listing of all ADA titer levels will be provided for participants with pre-existing, treatment-emergent and treatment-boosted ADA response.

5.10.2. Analysis of Neutralizing Antibody (NAb) Data

The absolute occurrence (n) and percent of participants (%) with NAb status in the NAb analysis set will be provided by treatment groups. The NAb status is categorized as follows:

- Negative: Samples tested negative in the ADA assay, or samples positive in the ADA assay but tested negative in the NAb assay.
- Positive: Samples tested positive in the NAb assay

5.11. Association of Immunogenicity with Exposure and Safety

5.11.1. Immunogenicity and Exposure

Potential association between immunogenicity and systemic exposure to casirivimab and imdevimab will be explored by treatment groups. Plots of individual casirivimab and imdevimab concentration time profiles may be provided to examine the potential impact of ADA category, maximum titer category and NAb status on these profiles.

5.11.2. Immunogenicity and Safety

Potential association between immunogenicity variables and safety may be explored with a primary focus on the following safety events during the TEAE period:

- Injection site reaction (serious or severe and lasting 24 hours or longer)
- Hypersensitivity (SMQ: Hypersensitivity [Narrow])
- Anaphylaxis (SMQ: Anaphylactic Reaction [Narrow])

The safety analyses mentioned above will be conducted using the following categories:

- ADA Positive
- Treatment-emergent
- Treatment-boosted
- Maximum post-baseline titer category in ADA positive participants
- NAb positive

6. DATA CONVENTIONS

The following analysis conventions will be used in the statistical analysis.

6.1. Definition of Baseline for Efficacy/Safety Variables

Unless otherwise specified, the Baseline assessment for all measurements will be the latest available valid measurement taken prior to the administration of investigational product.

6.2. Data Handling Convention for Efficacy Variables

Rules for handling missing RT-qPCR test results for primary and secondary efficacy variables are described in Section [5.7](#).

6.3. Data Handling Convention for Missing Data

This section includes the methods for missing data imputation and methods for missing mechanism exploration, if necessary. Missing data will not be imputed in listings. This section includes the methods for missing data imputation for some summary analyses, if necessary.

Date and Time of Study Treatment Injections

Since the study drug is administered at the site, the date and time of study drug administrations are filled in eCRF. No missing data is expected. The information is filled in eCRF. If a patient's date of the last dose is totally missing or unknown, his/her last visit date will be substituted.

Adverse Event

If the severity of a TEAE is missing, it will be classified as "severe" or "Grade 3" in the frequency tables by intensity of TEAEs. If the assessment of relationship of a TEAE to the investigational product is missing, it will be classified as related to study drug. When the partial AE date/time information does not indicate that the AE started prior to study treatment or after the TEAE period, the AE will be classified as treatment-emergent.

Medication/Procedure

If a medication date or time is missing or partially missing and it cannot be determined whether it was taken prior or concomitantly or stopped prior to the first study treatment administration, it will be considered as concomitant medication/procedure by imputing the start date on the date of first study treatment administration.

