#### **9.1.2. Footnotes for the Schedule of Events (Protocol Amendment 2)**

1. Approximately 85 days after the final dose of study drug (ie, the optional final dose of casirivimab+imdevimab defined in protocol amendment 2, or the final assigned casirivimab+imdevimab or placebo dose for participants who do not receive the optional dose).
2. Informed consent may be obtained at the dosing visit, or at any time prior to the visit via remote consent (if available and allowable at the study site).
3. Applicable to participants who consent to receive a final optional dose of 1200 mg SC casirivimab+imdevimab. The optional dose may be administered to all participants regardless of treatment assignment at randomization. However, participants will not be eligible to receive this dose if they have already received casirivimab+imdevimab as post-infection treatment. The dose will be recorded.
4. Vital signs (defined in Section [9.2.5.1](#)) will be collected before study drug administration and at least 60 minutes after completion of study drug administration.
5. Refer to Section [10.1](#) for AE monitoring and reporting guidelines.

6. Note that all assessments and procedures related to participants with suspected COVID-19 are optional for both the study site and the study participant. Refer to [Protocol Amendment 2 Procedures](#) for additional information.
7. Clinician assessment of sign or symptoms may occur remotely. If remote assessment is performed, a confirmatory site visit for laboratory testing of SARS-CoV-2 can optionally occur after a clinician deems that the signs or symptoms are related to COVID-19.
8. Comprehensive vital sign assessment includes standard vital sign assessment (defined in Section [9.2.5.1](#)), SpO2, and respiratory rate.
9. Note that samples for local and central laboratory testing of SARS-CoV-2 may be collected on the same day; the results of local testing are not required prior to sample collection for central testing.

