Post-Infection Treatment. Participants with confirmed positive SARS-CoV-2 RT-PCR will be eligible for post-infection treatment (as described in protocol Section 6.4.4) at any time prior to receipt of the optional 1200mg SC dose (eg, during the 4 weeks between receipt of the last protocol-defined dose and optional 1200 mg SC dose). Once this optional dose has been

administered, post-infection treatment will no longer be offered. Likewise, any participant who receives post-infection treatment will not be eligible to receive the optional 1200 mg SC dose.

Participants with Positive SARS-COV-2 RT-PCR. Participants with a positive SARS-CoV-2 RT-PCR may have additional assessments and sample collections, including unscheduled visits every 7

days (± 1 day) for central laboratory RT-qPCR analysis until 2 consecutive negative test results are obtained:

- NP swab samples for RT-qPCR
- COVID-19 signs and symptoms evaluated by the investigator or designee
- Information regarding COVID-19-related medically-attended visits (MAVs; defined in protocol Section 9.2.4.3)

End-of-Study Visit

All participants, including those who do not consent to receive the optional final dose, will have a follow-up (end-of-study) telephone visit approximately 85 days (3 months) from their last dose of investigational drug (casirivimab+imdevimab or placebo) to monitor safety. Study assessments for the 3-month follow-up visit will be limited to the collection of targeted adverse events, as detailed in the new schedule of events (protocol amendment 2 Table 2).

Sites will ensure that an additional discussion about the potential risks and benefits to the participant and fetus is discussed as part of re-consent for participants who become pregnant during the study.

Analysis Plan

At the time that enrollment was closed, 66 participants had been enrolled in the study. Due to the early study closure and the resulting small sample size of enrolled participants, all analyses will be performed descriptively and only numeric comparisons will be performed. All safety endpoints (including AEs, TEAEs, AESIs, SAEs, and safety laboratory values) will be summarized. Selected efficacy, virology, PK, and/or immunogenicity data may also be analyzed descriptively. No interim analysis will be performed for this study, and no IDMC review meetings will occur.

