5.6.2. Exposure to Investigational Product

The duration of study treatment exposure will be defined as day 1 through 4 weeks, ie, 28 days, after the last dose for a participant in the Q4W arms and day 1 through 12 weeks, ie, 84 days after the last dose for a participant in the Q12W arm. The duration of the study will be through the follow-up period defined as end of EAP through day 253 (± 14 days). Treatment exposure and study duration will be evaluated in the SAF.

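### SAP 6.3 replaces a missing last-dose date with the last visit date, which for a close-out completer is a telephone call about 85 days after the last dose and overstates that participant's exposure by as much

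*SAP*

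**What the plan says.** SAP 6.3, on the date and time of injections, starts from on-site dosing: "Since the study drug is administered at the site, the date and time of study drug administrations are filled in eCRF". It adds "No missing data is expected", and then gives a fallback: if a participant's "date of the last dose is totally missing or unknown, his/her last visit date will be substituted". Nothing restricts that visit to an on-site or dosing visit. SAP 4.6.1 treats the last study visit as the end of follow-up.

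SAP 1.1 gives all participants, including those who decline the optional dose, a "follow-up (end-of-study) telephone visit approximately 85 days (3 months) from their last dose of investigational drug". Protocol 9.1.2, footnote 1, times the same contact as "Approximately 85 days after the final dose of study drug", counted from the optional dose if it was taken and otherwise from the last assigned dose. The close-out schedule (Protocol Table 2, SAP Table 4) allows ±14 days.

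SAP 5.6.2 builds exposure on the last-dose date. For the Q4W arms: "The duration of study treatment exposure will be defined as day 1 through 4 weeks, ie, 28 days, after the last dose". For the other regimen: "day 1 through 12 weeks, ie, 84 days after the last dose for a participant in the Q12W arm".

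**The concern.** The fallback conflicts with the premise stated just before it. Drug is given at the site, so a telephone call cannot be a dosing date. For a participant who completes close-out, the rule nevertheless places the last dose on the day of the call. SAP 5.6.2 then adds a further 28 or 84 days.

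The error has a known direction and a nearly fixed size, because the call is itself timed from the last dose. With 16 to 17 participants per arm (SAP 2.1), a single such value is visible in an arm mean. The SAP describes the telephone visit in its own Section 1.1, so the information needed to write a workable rule was at hand.

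**Working it through.** The documents give no exposure total and no effect of the substitution, so there is no stated figure to reproduce. The check is date arithmetic.

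**Inputs**
- Tail added after the last dose: 28 days (Q4W arms, and placebo, which is given Q4W) or 84 days (Q12W arm), from SAP 5.6.2.
- Gap from last dose to end-of-study call: 85 days, or 85 − 14 = 71 to 85 + 14 = 99 over the window, from SAP 1.1 and SAP Table 4.
- Dosing days: 1, 29, 57, 85, 113 and 141, from the original schedule of events. The planned count is six Q4W or two Q12W doses (Protocol 3.2.2).
- Doses actually received: not stated, so a range is shown.

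**Check that the definition is read correctly.** Six Q4W doses end on day 141, and 141 + 28 = 169. Two Q12W doses end on day 85, and 85 + 84 = 169. Both reach day 169, the last visit of the efficacy assessment period.

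**Formulas.** With last dose on day L:
- true exposure = (L − 1) + tail
- exposure under the rule = true exposure + gap
- ratio = exposure under the rule / true exposure

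| Doses received | L | True (days) | Under the rule, gap 85 (days) | Ratio | Ratio, gap 71 to 99 |
|---|---|---|---|---|---|
| 1, Q4W | 1 | 28 | 113 | 4.0 | 3.5 to 4.5 |
| 2, Q4W | 29 | 56 | 141 | 2.5 | 2.3 to 2.8 |
| 3, Q4W | 57 | 84 | 169 | 2.0 | 1.8 to 2.2 |
| 4, Q4W | 85 | 112 | 197 | 1.8 | 1.6 to 1.9 |
| 5, Q4W | 113 | 140 | 225 | 1.6 | 1.5 to 1.7 |
| 6, Q4W | 141 | 168 | 253 | 1.5 | 1.4 to 1.6 |
| 1 active, Q12W | 1 | 84 | 169 | 2.0 | 1.8 to 2.2 |
| 2 active, Q12W | 85 | 168 | 253 | 1.5 | 1.4 to 1.6 |

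If the optional dose is counted as one more dose four weeks on, six Q4W doses plus the optional dose give 196 against 281 days, a ratio of 1.4. Counting days inclusively moves the ratios by about 0.1 at most.

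The Q12W rows assume that the last injection was an active one. If it was a blinding placebo injection, the gap from the last active dose would be longer.

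**Effect on an arm mean.** One affected participant adds 85/17 = 5.0 to 85/16 = 5.3 days. With 16.5 as the arm size, 85/16.5 = 5.15 days. That is 18% of a true mean of 28 days, 9% of 56 and 6% of 84.

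**Superseded schedule, for comparison.** The final contact was a call on day 253, which is 253 − 141 = 112 days after the last planned Q4W dose. For full dosing the ratio would have been (168 + 112)/168 = 1.7. The weakness therefore did not arise with Amendment 2.

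**The case against.** The strongest reply is that the rule may never be used. It applies only when the date is entirely missing, which the SAP does not expect. Dose dates also have several sources: unblinded staff enter administration in the EDC (Protocol 12.2.3), accountability records carry dispensing dates (8.8.3), and the optional dose is recorded (9.1.2, footnote 3). Moreover, a site that scheduled the call 85 days after the last dose must have known when that dose was given. Completers are thus the participants least likely to lack the date. All of this stands as to frequency. It does not make the substituted date a sensible one when the rule is used.

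The 85-day gap is also not universal. A participant who withdrew earlier may have a dosing visit as the last visit, with no error, or an early termination visit with some other gap. That stands too.

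A reader might further infer that efficacy data are affected, because SAP 4.5.1 removes data after a vaccine given within 90 days of the last dose. The documents do not show this. Take a vaccine t days after the true last dose and before an 85-day call. It lies t days from the true date and 85 − t days from the substituted one, both at most 85. If the 90 days are read as running either side of the dose, it falls inside the window both ways. Even with a call at day 99, its status changes only for t below 9 or above 90. A one-sided reading could give more changes, but the SAP does not say that it applies.

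The same section removes data after the optional dose. However, SAP 6.3 presents its imputations as serving some summary analyses and does not extend them to that cut-off.

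Finally, the safety observation periods run from the first dose to day 169 and then to the last visit (SAP 4.6.1), so they do not use the last-dose date. Listings are not imputed, and the continuous summaries include a median, which one outlying value barely moves.

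**Conclusion.** The rule is wrong as written for a participant who completes close-out and has no last-dose date: it overstates exposure by about 85 days (71 to 99). The ratio depends on how many doses were given. It is two-fold or more only after one to three Q4W doses or one active Q12W dose, and falls to about 1.5 at the full planned number. Few doses per participant is plausible given the early closure, but that is an assumption.

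A reader might infer that the trial's exposure is overstated two- to four-fold in general. The documents do not support that. They report no missing date, and a participant with a recorded date is unaffected.

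The point is minor. It bears on one descriptive summary in a study of 66 participants whose endpoints have all been designated exploratory (SAP 1).

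**What to change.** Replace the substitution sentence in SAP 6.3 with: *If the date of the last dose is missing, substitute the date of the last on-site visit at which study drug administration was recorded or, if there is no such record, the last on-site visit at which a dose was scheduled; telephone and follow-up visits are not used.*

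The first part covers a blank dose-date field at a visit where administration was otherwise recorded. The second part is needed so that the rule still gives an answer when no such record exists. It can still be wrong if the scheduled dose was not given: by about one dosing interval (28 days) if only that last dose was omitted, against about 85 days under the present rule.

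The cost is one SAP sentence and the matching line of programming. It needs visit dates and administration records that the study already collects, and no new data.
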